9.1 Discontinuation

9.1.1 Discontinuation of study treatment

Discontinuation of study treatment for a subject occurs when study treatment is stopped earlier than the protocol planned duration, and can be initiated by either the subject or the investigator.

The investigator must discontinue study treatment for a given subject if, he/she believes that continuation would negatively impact the subject's well-being.

Study treatment must be discontinued under the following circumstances:

- Disease progression
- Unacceptable adverse event, including meeting stopping criteria as described in Section 6.5.2
- Subject/guardian decision
- Pregnancy
- Use of prohibited treatment as per recommendations in Section 6.2.3
- Any situation in which study participation might result in a safety risk to the subject.

If discontinuation of study treatment occurs, the investigator should make a reasonable effort to understand the primary reason for the subject's premature discontinuation of study treatment and record this information.

In extraordinary situations due to the very short half-life of radionuclides, e.g. a sudden temporary supply disruption and/or a quality finding after release of the product, the investigator may immediately be:

- 1. advised on how to manage participants in screening or on treatment;
- 2. informed to withhold doses from impacted batch and not administer them to the participant;

and/or

3. asked to closely monitor participants who have received a dose from an impacted batch for adverse events.

Subjects who discontinue study treatment or who decide they do not wish to participate in the study further should NOT be considered withdrawn from the study UNLESS they withdraw their consent. Where possible, they should return for the assessments indicated in the assessment schedule. If they fail to return for these assessments for unknown reasons, every effort (e.g. telephone, e-mail, letter) should be made to contact the subject/predesignated contact as specified in the lost to follow-up section (Section 9.1.3). This contact should preferably be done according to the study visit schedule.

If the subject cannot or is unwilling to attend any visit(s), the site staff should maintain regular telephone contact with the subject, or with a person pre-designated by the subject. This telephone contact should preferably be done according to the study visit schedule.

After study treatment discontinuation, at a minimum, in abbreviated visits, the following data should be collected at clinic visits or via telephone/email contact (per assessment schedule in Table 8-3 and Table 8-4):

- new / concomitant treatments including any radiotherapy, surgical procedure or new anticancer therapy
- adverse events/Serious Adverse Events
- survival status

During the COVID-19 pandemic, for patients who are unable to come to the study site for their scheduled visit, conducting patient study visits on schedule by telephone may be possible. As patient safety is the number one concern, patients may need to discontinue treatment based on the investigator's clinical judgment or patient's own decision. The investigator should document in the source notes as clearly as possible the decisions made around continuing or discontinuing study treatment for a patient and the risk-benefit for each case as it may arise. The investigator should consider if alternative therapeutic options exist and may be warranted based on the individual benefit-risk for the patient.

9.1.1.1 Replacement policy

Not applicable. Subjects will not be replaced on study.

A subject can be re-screened with a new study number when intercurrent conditions emerging after consent signature and impeding the planned randomization are resolved. Such cases must be discussed and approved by the Sponsor. The site will be informed about the procedures to be followed for re-screening.

9.1.2 Withdrawal of informed consent

Withdrawal of consent/opposition to use of data and/or biological samples occurs in countries where the legal justification to collect and process the data is based on consent and when a participant:

- Explicitly requests to stop use of their data and
- No longer wishes to receive study treatment
- and
- Does not want any further visits or assessments (including further study-related contacts)

In this situation, the investigator should make a reasonable effort (e.g. telephone, e-mail, letter) to understand the primary reason for the subject's decision to withdraw his/her consent and record this information.

Study treatment must be discontinued, and no further assessments conducted, and the data that would have been collected at subsequent visits will be considered missing. All efforts should be made to have any study drug returned to the Investigator.

Further attempts to contact the subject are not allowed unless safety findings require communicating or follow-up. All efforts should be made to complete the assessments prior to study withdrawal. A final evaluation at the time of the subject's study withdrawal should be made as detailed in the assessment table.

Advanced Accelerator Applications will continue to retain and use all research results (data) that have already been collected for the study evaluation.

9.1.3 Lost to follow-up

For subjects whose status is unclear because they fail to appear for study visits without stating an intention to discontinue or withdraw, the investigator must show "due diligence" by documenting in the source documents steps taken to contact the subject, e.g. dates of telephone calls, registered letters, etc. A subject should not be considered as lost to follow-up until due diligence has been completed or until the end of the study.

9.1.4 Early study termination by the sponsor

The study can be terminated by Advanced Accelerator Applications at any time for any reason. This may include reasons related to the benefit/ risk assessment of participating in the study, practical reasons (including slow enrollment), or for regulatory or medical reasons. In taking the decision to terminate, Advanced Accelerator Applications will always consider the subject welfare and safety. Should early termination be necessary, subjects must be seen as soon as possible (provide instruction for contacting the subject, when the subject should stop taking drug, when the subject should come for a final visit) and treated as a prematurely withdrawn subject. The investigator may be informed of additional procedures to be followed in order to ensure that adequate consideration is given to the protection of the subject's interests. The investigator or sponsor depending on the local regulation will be responsible for informing IRBs/IECs of the early termination of the trial.

9.2 Study completion and post-study treatment

Subjects will be followed during the study per the schedule of assessments (refer to Table 8-3 and Table 8-4).

Before the PFS primary analysis (99 evaluable and centrally confirmed disease progressions or death events), patients continue the Treatment Phase until progression; after the PFS primary analysis, the Treatment Phase duration becomes fixed (72 weeks).

Following the end of treatment or early treatment discontinuation, alive patients will enter in the Follow up Phase unless unfeasible (e.g. consent withdrawal, patient lost to follow-up). All treated subjects should have a safety follow up visit conducted 30 days after last administration of study treatment (EoT visit). The information collected is kept as source documentation. Documentation of attempts to contact the subject should be recorded in the source documentation.

At any time during the study (before or after the primary End-Point analysis) any progressive patient (based on central imaging assessment) immediately ceases the Treatment Phase and proceeds to the Follow-up Phase assessment.

Patients randomized in the control arm have the option to enroll for post-progression cross-over upon signature of a new consent (optional Treatment Extension Phase) and receive maximum 4 cycles of Lutathera (7.4 GBq / 200 mCi x 4 cycles; cumulative dose: 29.6 MBq / 800mCi) plus octreotide long-acting every 8 weeks. For these patients, the EoT visit and evaluation of cross-over eligibility can occur on the same day. If these two visits are done on separate days, EoT can be done remotely by phone, and all applicable assessments can be done at the cross-over eligibility visit. If a patient continues to cross-over, 28-day window for EoT visit does not need to apply.

Patients randomized in the Lutathera arm have the option to enroll for post-progression Retreatment Phase upon signature of a new consent and receive 2-4 additional cycles of Lutathera (7.4 GBq / 200 mCi) every 8 weeks. Re-treatment Phase will last until a locally confirmed disease progression or until EoS, whichever occurs first.

The control arm patients who will consent to post-progression cross-over with Lutathera, and the Lutathera arm patients who will consent to post-progression re-treatment with Lutathera, will continue study assessments as planned in Table 8-4; these patients will enter in the Follow up Phase after the end of Lutathera treatment.

The End of Study (EOS) is when 4 years have elapsed from the randomization of the last patient, or 6 months after the last cross-over or re-treatment dose, whichever occurs last. The time window to start cross-over/re-treatment is further discussed in Sections 5.2.1, 5.2.2 and 9.2.1.

At the End of Treatment (EOT) or End of Study (EOS) or early discontinuation visit, any repeat assessments associated with this visit should have been documented and followed-up appropriately by the Investigator, or in the event of an early study termination decision, the date and reason of that decision.

At the EoT, a CT/MRI scan for RECIST assessment is required only if not taken in the previous 12 weeks. If no post-baseline scan is available, a scan is needed at EoT. At the EoS, a CT/MRI scan for RECIST assessment is required only if a scan was not taken in the previous 6 months.

Each subject will complete their EOS visit at the end of the study (after 3 years of follow up from the end of the Treatment Phase, at early withdrawal from the study, death, withdrawal of consent, lost to follow-up or when the end of study is communicated by Sponsor). The last 6-monthly follow-up visit will be considered EOS visit, when all assessments need to be performed as indicated in the Assessment Schedule for EOS.

Post relapse therapy will be permitted during the study in the Follow-up Period per Investigator discretion, but not provided or administered as study treatment.

The final OS analysis will be performed when the last subject completes their EOS visit. All available data from all subjects up to this cut-off date will be analyzed. All adverse events during the study period must be reported as described in Section 10.

In the event the study is terminated due to futility, study subjects currently on study treatment in the Treatment Phase and who are still deriving clinical benefit will be eligible to continue their Lutathera treatment through a locally established Advanced Accelerator Applications program. Lutathera treatment through a locally established Advanced Accelerator Applications program will not be part of this clinical trial and will follow the applicable local regulations.

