	period. Assessments will be continued until disease progression documented by investigator or until End of Study, whichever occurs first				
	Follow up Phase				
	At the end of the Treatment Phase or after discontinuation for any cause (including disease progression), all patients will continue to be followed up to 3 years to continue data collection for the secondary endpoints of the study, such as long term safety and overall survival. Patients included in the optional crossover or re-treatment phase will be followed up at least 6 months and up to 3 years (or until EoS, whatever comes first).				
	During the Follow-up Phase, serious adverse events and adverse events of special interest (AESI) related to the study treatment as well as AESI of secondary hematological malignancies irrespective of causality, will be reported. Anti-tumor treatments administered after progression/discontinuation, disease status based on local CT/MRI assessment, and OS data will be collected every 6 months in both arms.				
	End of the Study				
	The End of Study is after 4 years have elapsed from the randomization of the last patient or 6 months after the last cross-over or re-treatment dose in the study, whichever occurs last. The time window to start cross-over or re- treatment with Lutathera in this study is within 4 years after the last patient has been randomized. For patients in the Lutathera arm who progress beyond this window, access to re-treatment with Lutathera may be granted via Post Study Drug Supply (PSDS) programs.				
Population	In this study, safety and efficacy of treatment with Lutathera plus octreotide long-acting (30 mg) versus high dose octreotide long-acting (60 mg) is evaluated in patients \geq 15 years with somatostatin receptor positive, wel differentiated G2 (Ki67 index \geq 10% to \leq 20%) and G3 (Ki67 > 20% and \leq 55%) advanced GEP-NETs. Patients with documented RECIST progression to previous treatments for the current GEP-NET at any time prior to randomization are not eligible to participate in this study.				
Key Inclusion	Subjects eligible for inclusion in this study must meet all of the following criteria:				
	1. Presence of metastasized or locally advanced, inoperable (curative intent) histologically proven, well differentiated Grade 2 or Grade 3 gastroenteropancreatic neuroendocrine (GEP-NET) tumor diagnosed within 6 months prior to screening.				
criteria	2. Ki67 index ≥ 10 and $\le 55\%$.				

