Pharmacokinetic assessments	Patients in the control arm (all countries except for China) will yield PK data from blood sampling performed at pre-dose with respect to the octreotide long-acting i.m. injection for the 2nd, 4th, 5th and 7th treatment cycle (that is respectively at week 4, 12, 16 and 24) for the determination of plasma trough levels. Data will be processed using a population based model, for exploratory purposes.

Key safety assessments	All adverse events (AEs), whether or not spontaneously reported by the patient, will be recorded starting from the signing of the ICF until the end of the Treatment Phase/optional Treatment Extension Phase in case of cross-over/optional re-treatment. During the Follow up Phase only related serious adverse events and related AESI other than secondary hematological malignancies will be recorded. AESI of secondary hematological malignancies will be recorded during the whole study irrespective of causality.
Data analysis	The primary efficacy and safety analyses will be performed after observing approximately 99 PFS events. At that time a soft database lock will ensure the integrity of the data and make further data entry for the continuation of the trial possible.
	The primary endpoint of the study is progression-free survival (PFS), defined as the time from the date of randomization to the date of the first documented progression or death due to any cause. PFS will be assessed via central review according to RECIST 1.1.
	The following statistical hypotheses will be tested to address the primary efficacy objective:
	H_{01} (null hypotheses): $\Theta_1 \ge 0$ vs. H_{a1} (alternative hypotheses): $\Theta_1 < 0$
	Where Θ_1 is the log hazard ratio of PFS in the Lutathera plus Standard Dose octreotide long-acting (30 mg) (investigational) arm vs. High Dose octreotide long-acting (60 mg) (control) arm.
	The primary efficacy analysis to test this hypothesis and compare the two treatment groups will consist of a stratified log-rank test at an overall one- sided 2.5% level of significance in favor of the Lutathera plus Standard Dose octreotide long-acting (30 mg) arm. The stratification will be based on the following randomization stratification factors (grade: G2 vs. G3; and tumor origin: pNET vs other origin).

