3.4 Optional Re-Treatment Phase

In the Lutathera arm, patients with radiological progression based on RECIST criteria as per central assessment have the option to enroll for post-progression re-treatment, upon signature of a new informed consent, to receive 2 to 4 additional cycles of 7.4 GBq/200 mCi of Lutathera. If RECIST progression occurs after Week 72 post the primary end point analysis, the decision to enroll the patient in re-treatment will be based on local assessment.

Patients who have received Lutathera in Optional Treatment Extension Phase (cross-over) are not eligible for re-treatment with Lutathera.

For enrolment in the optional re-treatment phase, patients must undergo SSTR imaging and meet all requirements listed in Section 5.2.2.

After enrolment into re-treatment phase, patients will initially receive 2 administrations of Lutathera 7.4 GBq/200 mCi at 8-week interval. After that, the Investigator should determine if:

- The patient shows evidence of disease stabilization or response (i.e. absence of radiological progression, or assessed by clinical benefit).
- Has shown good tolerance to Lutathera re-treatment.

If the investigator considers this treatment option in the best interest of the participant and if the participant meets these criteria and agrees to continue with further treatment with Lutathera, the Investigator may administer up to 2 additional administrations of Lutathera 7.4 GBq/200 mCi at 8-week interval. A maximum of 4 administrations of Lutathera is allowed during the re-treatment period.

All safety and efficacy assessments in the re-treatment period will be performed locally and following the schedule in initial treatment period (expression of somatostatin receptors on all target lesions will be evaluated locally before re-treatment; there is no central 'real time' assessment of the SRI images, however the images should be submitted to the central imaging center possibly within 1 month for a second review).

During the re-treatment phase, the administration of SSAs is at investigator's discretion.

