The re-treatment phase will last until locally confirmed disease progression or until EoS, whichever occurs first. If a patient discontinues Lutathera before locally confirmed disease progression in re-treatment, the patient should be followed with tumor assessments as per initial CT/MRI schedule until locally confirmed disease progression. After re-treatment phase is complete, patients will be followed up for 3 years or until EoS, whichever occurs first (and at least 6 months after the last re-treatment dose in the study).

The time window to start re-treatment in this study is within 4 years after the last patient randomized.

For patients in Lutathera arm who are eligible for re-treatment beyond this window, Lutathera access for re-treatment may be granted via Post Study Drug Supply (PSDS) programs, based on local regulation (see Section 9.2.1).

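### One paragraph of protocol 9.2 applies the cross-over rule to re-treated patients and moves them to Follow-up when Lutathera ends, against 3.4 and the synopsis (internal inconsistency, low severity)

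*Protocol*

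**What the plan says.** The paragraph at issue is in protocol 9.2, just before the definition of End of Study. It names cross-over and re-treated patients together, says that they "will continue study assessments as planned in Table 8-4", and ends: "these patients will enter in the Follow up Phase after the end of Lutathera treatment".

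Other places set the end of re-treatment differently:

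- **9.2, preceding paragraph:** "Re-treatment Phase will last until a locally confirmed disease progression or until EoS, whichever occurs first".
- **Synopsis, Optional Re-treatment Phase:** "Assessments will be continued until disease progression documented by investigator or until End of Study, whichever occurs first", on the schedule of the initial treatment period.
- **3.4:** "All safety and efficacy assessments in the re-treatment period will be performed locally and following the schedule in initial treatment period". If Lutathera is stopped before local progression, "the patient should be followed with tumor assessments as per initial CT/MRI schedule until locally confirmed disease progression".
- **Table 8-3, re-treatment column:** assessments run until progression, then the EoT visit, then follow-up. End of study is not named. Footnote 10 lists visits up to W68.
- **12.6.4:** the re-treatment period runs from the first re-treatment dose to progression or death.

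For cross-over, section 3.3 ends the phase after four doses, with EoT at Week 28 and then follow-up. The cross-over column of Table 8-4 points back to Table 8-3 assessments but stops them at Week 24.

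**The concern.** Re-treatment is 2 to 4 doses at 8-week intervals, so on schedule the last dose falls between about W8 and W24. The phase itself ends at local progression or end of study. A re-treated patient who has finished Lutathera without progressing therefore falls under two rules: Follow-up by one paragraph of 9.2, and the initial schedule by 3.4 and the synopsis.

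The two rules collect different data. On the initial schedule, scans are at W16, W24 and then every 12 weeks; in Follow-up they are every 6 months. The synopsis records all adverse events "until the end of the Treatment Phase/optional Treatment Extension Phase in case of cross-over/optional re-treatment", whereas in Follow-up section 8.5.1 records only related SAEs and related AESI, plus secondary haematological malignancies whatever their cause. If sites read different sections, the re-treatment PFS, duration of response and safety summaries would mix two collection schemes, and scans or events not collected on time cannot be recovered.

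**Working it through.** The plan states no figure on this point, so there is none to reproduce. The check has two parts.

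**1. Which rule is intended**

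| Source | End of phase or assessments for re-treated patients |
|---|---|
| 9.2, paragraph at issue | End of Lutathera |
| 9.2, preceding paragraph | Local progression or EoS |
| Synopsis | Investigator-documented progression or EoS |
| 3.4 | Local progression or EoS; initial scan schedule continues if Lutathera stops early |
| Table 8-3, re-treatment column | Progression |
| 12.6.4 | Progression or death |

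The paragraph at issue matches 3.3, the cross-over rule. Its table reference points the same way: Table 8-4 is the control-arm table, and the re-treatment column is in Table 8-3. Reading the end of Lutathera treatment as the end of the Re-treatment Phase does not help, because 3.4 treats stopping Lutathera and ending the phase as separate events.

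**2. Effect on the timing of detected progression**

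Inputs:

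- PFS from the first re-treatment dose is exponential, with medians of 8, 12.52 and 18 months. The protocol gives 12.52 from the re-treatment meta-analysis (4.1); 8 and 18 are an assumed range.
- With 30.4375 / 7 weeks per month, the medians are 34.79, 54.44 and 78.27 weeks.
- Time runs from the first re-treatment dose (8.3.1). Progression is dated to the first scheduled scan at or after it.
- Schedule A (3.4): W16, W24, then every 12 weeks.
- Schedule B, four doses (paragraph at issue): W16, W24, EoT at W28 without a new scan, then W54 (28 + 26) and every 26 weeks.
- Schedule B, two doses: EoT scan at W12 (8 + 4), then every 26 weeks.

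Write S(t) = exp(-λt) and λ = ln 2 / median. Mean delay is mean detected time minus mean true time (1/λ):

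- A: 16 + 8·S(16) + 12·S(24) / [1 - S(12)] - 1/λ
- B, four doses: 16 + 8·S(16) + 30·S(24) + 26·S(54) / [1 - S(26)] - 1/λ
- B, two doses: 12 + 26·S(12) / [1 - S(26)] - 1/λ

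At a median of 12.52 months, λ = 0.01273 and 1/λ = 78.54. S(12), S(16), S(24), S(26) and S(54) are 0.8583, 0.8157, 0.7367, 0.7182 and 0.5028. Unrounded, A gives 6.38 weeks, B with four doses 12.47 and B with two doses 12.64.

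| Median (months) | A | B, 4 doses | B, 2 doses | B - A, 4 doses | B - A, 2 doses |
|---|---|---|---|---|---|
| 8 | 6.61 | 12.15 | 12.44 | 5.54 | 5.83 |
| 12.52 | 6.38 | 12.47 | 12.64 | 6.09 | 6.27 |
| 18 | 6.26 | 12.64 | 12.75 | 6.39 | 6.49 |

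Differences are taken before rounding. Detection is 5.5 to 6.5 weeks later.

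If a share q of progressions is imaged at once on clinical suspicion (8.3.1), the difference is multiplied by 1 - q. For q = 0.25 it is 4.2 to 4.9 weeks; for q = 0.5 it is 2.8 to 3.2 weeks.

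The four-dose column applies that schedule to all re-treated patients. Doses 3 and 4 are conditional (3.4: "The patient shows evidence of disease stabilization or response"), so actual four-dose patients are a selected group.

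**Adverse events.** The share still progression-free 30 days after a fourth dose at W24 (24 + 30/7 = 28.29 weeks) is exp(-ln 2 × 28.29 / median) = 57%, 70% and 78% for the three medians, counted from the first re-treatment dose. These are the patients for whom recording would narrow before progression.

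**The case against.** The strongest reply is that the right rule is stated in several other places, including the paragraph just before. Section 9.2 opens by sending sites to Tables 8-3 and 8-4, the Table 8-3 column and footnote 10 carry re-treatment visits well past any fourth dose given on schedule, and Amendment 2.0 clarified that scans continue after Lutathera stops. A site would have to overlook all of this, and nothing in the documents says how likely that is. This stands: the intended design is clear, and every delay above is conditional on a site following the outlier. It does not remove the conflict, because the outlier is operative body text and names re-treated patients explicitly.

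The effect on planned output is also small, and this stands too. SAP 2.1.1.10 ends the re-treatment period for adverse events at last dose + 30 days, so those tables are largely unaffected. Protocol 10.1.6 already limits SAE reporting after 30 days to related events and secondary haematological malignancies.

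A reader might infer that primary PFS or its event count is at risk. The documents do not support that. Re-treatment follows progression in the randomised phase, the primary estimand censors PFS at re-treatment that precedes a central event, and SAP 2.1.1.10 defers re-treatment efficacy analyses beyond the primary PFS analysis.

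A reader might also infer that the observed median re-treatment PFS shifts by the delay shown. The calculation gives a mean delay, not a shift in the median. Nor does it describe patients cut off by end of study, where 9.2 requires a scan only if none was taken in the previous 6 months.

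**Conclusion.** The paragraph is wrong as written for re-treated patients. It is an internal inconsistency of low severity; the design itself is not in question. A site following it would more than double the scheduled interval between local scans (12 weeks to about 26) and narrow adverse event recording before progression. The 5.5 to 6.5 week delay rests on exponential PFS, the assumed range of medians and scheduled scans only, and it shrinks with prompt imaging. The endpoints touched are exploratory, descriptive and locally assessed. The 99 events, the 222 patients and the type I error control are unaffected.

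**What to change.** - In the 9.2 paragraph that groups the two sets of patients, limit the Table 8-4 reference and the Follow-up clause to cross-over patients.
- Add: *Re-treated patients follow Table 8-3 until locally confirmed progression or EoS, whichever occurs first, including when Lutathera is stopped early, and then enter the Follow-up Phase.*
- Two general clauses would otherwise leave the conflict in place for patients who stop Lutathera early: the 9.2 sentence sending living patients to Follow-up after treatment ends or is stopped, and the matching clause in 3.5 on discontinuation for any cause. Add to each: *except re-treated patients without locally confirmed progression (see 3.4)*.

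The cost is a text correction. Section 14.1 requires a written, approved amendment for any protocol change, so include it in the next one. It adds no visits beyond those already in Table 8-3.
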